11.2.2. Schedule of Assessments for Subjects Who Permanently Discontinue Investigational Product

Procedure	Continue Scheduled Clinic Visit (Weeks 4, 8, 12,16,20) ^{4,5}	Week 26 (Equivalent to End of Treatment Visit)	Follow-up Week 34
Full (F) or brief (B) physical exam	B	F	F
Weight	X	X	X
12-lead ECG ¹		X	X
Vital Signs	X	X	X
Clinical chemistry/hematology samples ²	X	X	X
HbA1c and FPG ³	X	X	X
Review AE/SAE, concomitant medication and hypoglycaemia events	X	X	X

1. 12-lead ECGs will be obtained **before** measurement of vital signs and collection of blood samples for laboratory testing. Vital signs measurement will be taken before collection of blood sample. See Protocol Section 7.4.5.
2. Clinical chemistry and hematology assessments are described in Protocol Section 7.4.6.
3. Subjects will have their FPG and HbA1c levels evaluated to monitor for potential hyperglycemia.
4. Week will be dependent on when the subject discontinues investigational product. Subjects will start this schedule as soon as possible following investigational product discontinuation and timings of visits will be the same as for if the subject was continuing on investigational product. The timing of the clinic visits can be modified at the discretion of the investigator. All subjects must attend the Week 26 visit.
5. Additional unscheduled visits will occur as medically necessary.

11.3. Appendix 3: Assessment Windows

11.3.1. Definitions of Baseline and Study Day

In general, the baseline value for each variable will be defined as the last measurement collected prior to the first dose of randomized study medication.

Study day will be defined as the number of days from the first dose of randomized study medication. The date when a subject receives the first dose of randomized study medication is defined as Day 1. For events after the first dose date, study day is calculated as the difference in days between the first dose date and the date of interest, plus 1 day. For events that occur before the first dose date, study day is calculated as the difference in days between the first dose date and the date of interest. Thus, the day before first dose date is defined as Day -1.

Note that the date of first dose is Day 1 and the day before the date of first dose is Day -1 (there is no Day 0).

11.3.2. Visit Slotting Algorithm

For all safety and efficacy parameters to be summarized or analyzed by visit, data records will be slotted to one of the protocol specified visits using the following algorithm:

- a) Determine the therapy period and study day for all records using the algorithms from [Appendix 4: Treatment Periods](#).
- b) For all records (including unscheduled visit records, early withdrawal records and repeat visit records), use the therapy period and study day determined above with the slotting intervals in the respective Table Analysis Visit Windows below to slot the record to the appropriate analysis visit.

Safety assessments:

- For records determined to be in the pre-therapy period, the Screening (Week -2) and Baseline (Week 0) analysis visits will be based on the nominal visits recorded on the eCRF.
- For records determined to be in the on-therapy period, use the study day with the slotting intervals in the respective table below to assign the records to the appropriate on-therapy analysis visit (Week 1 through Week 26).
- For records determined to be in the post-therapy period, the study day will not be used for assigning the analysis visit. Instead, all post-therapy period records for subjects who complete randomized study treatment according to protocol will be assigned to the Week 34 post-therapy analysis visit. For subjects who terminate study treatment early, all post-therapy period records will be assigned to the 8 Week Follow up Visit.

Efficacy assessments (HbA1c and FPG):

- For records determined to be in the pre-therapy period, the Screening (Week -2) and Baseline (Week 0) analysis visits will be based on the nominal visits recorded on the eCRF.
- For records determined to be in the on-therapy or post-therapy period, use the study day with the slotting intervals in the respective table below to assign the records to the appropriate on-therapy analysis visit (Week 1 through Week 34).

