9.4.5.3. Reasons for Withdrawal

Reasons for withdrawal from the study are lost to follow-up or withdrawal consent. All subjects who discontinuation from investigational product due to the reasons listed under Section 5.5 will remain in the study and efficacy and safety data will be collected.

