11.3.3. Multiple Evaluations

After all the records have been slotted based on therapy period and study day, if there are multiple valid records for an assessment within an assigned analysis visit, only one of these records will be used for summary statistics and analyses. The record to be used is determined using the following hierarchy (in decreasing order of priority):

- the record closest to the target visit day
- the record with an original nominal visit that matches the analysis visit
- the record earliest in time for post-baseline assessments; for baseline, it is the record latest in time

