
* Week 26 is the end of treatment visit for those subjects completing the study per-protocol. For subjects who withdraw early from study treatment, the end of treatment visit will be assigned to an analysis visit based on the visit slotting algorithm using study day and therapy phase.
 
** Week 34 is the 8 week post-treatment follow-up visit for those subjects completing the study per-protocol. The 8 Week Follow-up Visit is the 8 week post-treatment follow-up visit for those subjects who withdraw early from study treatment. Both visits will be assigned based on the visit slotting algorithm using therapy phase.
 
*** The target study day for the 8 Week Follow-up Visit for subjects who withdraw early from study treatment is set to be 9 weeks (63 days) after last dose to correspond with the timing of the 8 week post-treatment follow-up for subjects completing the study per-protocol (where last dose is at Week 25 and the follow-up visit is at Week 34).
		

For HbA1C assessments:

Scheduled Visit	Target Study Day of Visit	Slotting Intervals
Pre-therapy		
Week -2	-14	Not applicable
Baseline (Week 0)	1	Not applicable
On-therapy or post-therapy*		
Week 1	8	2 to 18 days
Week 4	29	19 to 43 days
Week 8	57	44 to 71 days
Week 12	85	72 to 99 days
Week 16	113	100 to 127 days
Week 20	141	128 to 162 days
Week 26 (End of Treatment Visit)	183	163 to 211 days
Week 34	239	>211 days

* For all subjects regardless their study drug discontinuation status, their on-therapy or post-therapy period assessments will be slotted in the same way to the appropriate analysis visits per the above defined slotting intervals.
		

For FPG assessments:

Scheduled Visit	Target Study Day of Visit	Slotting Intervals
Pre-therapy		
Baseline (Week 0)	1	Not applicable
On-therapy or post-therapy*		
Week 1	8	2 to 11 days
Week 2	15	12 to 18 days
Week 3	22	19 to 25 days
Week 4	29	26 to 32 days
Week 5	36	33 to 39 days

Scheduled Visit	Target Study Day of Visit	Slotting Intervals
Week 6	43	40 to 46 days
Week 7	50	47 to 53 days
Week 8	57	54 to 60 days
Week 9	64	61 to 67 days
Week 10	71	68 to 74 days
Week 11	78	75 to 81 days
Week 12	85	82 to 88 days
Week 13	92	89 to 102 days
Week 16	113	103 to 127 days
Week 20	141	128 to 162 days
Week 26 (End of Treatment Visit)	183	163 to 211 days
Week 34	239	>211 days

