11.4. Appendix 4: Treatment Periods

For classifying AEs (including hypoglycemic events), the therapy periods will be defined as:

- **Pre-therapy:** The onset date of the AE is before the start date of randomized study medication. If the onset date of the AE is on the start date of randomized study medication, the AE will be considered as on-therapy.
- **On-therapy:** The onset date of the AE is on or after the start date of randomized study medication and within 25 days after the date of last dose.
- **Post-therapy:** The onset date of the AE is more than 25 days after the last date of randomized study medication.

For immunogenicity data and other safety parameters that are assessed prior to administration of randomized study medication on dosing days, the therapy periods will be defined as:

- **Pre-therapy:** The assessment date is on or before the start date of randomized study medication.
- **On-therapy:** The assessment date is after the start date of randomized study medication and within 25 days after the date of last dose.
- **Post-therapy:** The assessment date is more than 25 days after the last date of randomized study medication.

For an AE with an incomplete start date where the year and month are present while the day is missing, or where the year is present while both month and day are missing, the date is imputed in a dynamic way consistent with the partial date information so that the resulting AE therapy period assignment based on the imputed date is the most conservative possible, where the order from the most to the least conservative is: on-therapy phase > post-therapy phase > pre-therapy. Note that if the AE stop date is present, then the imputed start date will always be on or prior to the stop date.

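### In subjects who stop product early, by-visit safety summaries reduce all records more than 25 days after last dose to one 8 Week Follow-up record, and Week 26 leaves its own row for any last dose at Week 22 or earlier

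*SAP*

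**What the plan says.** Subjects who stop product early are followed, not dropped. Protocol 9.4.5.3 says they "will remain in the study and efficacy and safety data will be collected". Protocol Table 5, repeated in SAP 11.2.2, gives them vital signs, weight and chemistry/hematology at whichever of Weeks 4, 8, 12, 16, 20, 26 and 34 still lie ahead, and an ECG at Weeks 26 and 34. Its notes add: "All subjects must attend the Week 26 visit".

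Four SAP provisions decide where those records go.

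- **Therapy period (11.4).** A safety record is post-therapy when this holds: "The assessment date is more than 25 days after the last date of randomized study medication".
- **Slotting (11.3.2, safety).** "For records determined to be in the post-therapy period, the study day will not be used for assigning the analysis visit". The next rule covers early stoppers: "For subjects who terminate study treatment early, all post-therapy period records will be assigned to the 8 Week Follow up Visit".
- **Target day (11.3.4).** The 8 Week Follow-up slot is centred on last dose + 63 days in the vital-sign, ECG, lab and weight tables.
- **Selection (11.3.3).** If a slot holds several valid records, "only one of these records will be used for summary statistics and analyses". The first criterion is closeness to the target day.

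HbA1c and FPG are treated differently. Under their windows in 11.3.4: "For all subjects regardless their study drug discontinuation status, their on-therapy or post-therapy period assessments will be slotted in the same way".

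**The concern.** The rule and the visit schedule do not fit together. Table 5 contains no visit timed at 8 or 9 weeks after last dose. It has the ordinary calendar visits and a Week 34 follow-up. A rule that ignores study day puts up to seven scheduled visits into one slot, uses one, and gives it a label that describes its timing only by chance.

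Laboratory evaluations, vital signs and ECGs are named secondary safety endpoints. By-visit displays such as Tables 3.221 to 3.227, 3.231 to 3.233 and 3.341 to 3.343, and Table 3.344 (ECG shift from baseline to Week 26), draw on the selected record only. The rule also covers unscheduled records, so repeat chemistries after a liver stopping event, if held as lab records, meet the same limit once 25 days have passed. Finally, Week 26 would describe one set of subjects in the safety tables and a wider set in the HbA1c and FPG tables.

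**Working it through.** **Inputs.** Table 5 visits: Weeks 4, 8, 12, 16, 20, 26, 34 (Protocol Table 5; SAP 11.2.2). On-therapy limit: last dose + 25 days (SAP 11.4). Target: last dose + 63 days (SAP 11.3.4). One record used per slot (SAP 11.3.3). Study day of Week w = 7w + 1 (SAP 11.3.1 and 11.3.4).

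**The plan's own figure.** Week 25 is day 7 × 25 + 1 = 176 and Week 34 is day 7 × 34 + 1 = 239. The difference is 63 days, as stated.

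**Rule applied.** For last dose on day L, a later visit on day V keeps its study-day slot if V − L ≤ 25. Otherwise it joins the 8 Week Follow-up slot, where the record with the smallest |V − (L + 63)| is used. Visits are taken on their nominal day, and ties go to the earlier record.

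**Example, last dose Week 6 (day 43), target day 106.** Week 8 (day 57) is 14 days after last dose and keeps its slot. Weeks 12, 16, 20, 26 and 34 (days 85, 113, 141, 183, 239) are collapsed. Their distances from day 106 are 21, 7, 35, 77 and 133. Week 16 is used and the other four are not.

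**Vital signs, weight and labs, by week of last dose** (counts are per stop week)

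| Last dose | Visits collapsed | Visit used | Unused | Week 26 record |
|---|---|---|---|---|
| Week 0 | 7 | Week 8 | 6 | unused |
| Weeks 1-4 | 6 | Week 8 (stop Week 1, tie) or 12 | 5 | unused |
| Weeks 5-8 | 5 | Week 12 (stop Week 5, tie) or 16 | 4 | unused |
| Weeks 9-12 | 4 | Week 16 (stop Week 9, tie) or 20 | 3 | unused |
| Weeks 13-14 | 3 | Week 20 (stop Week 14, tie with Week 26) | 2 | unused |
| Weeks 15-16 | 3 | Week 26 | 2 | relabelled |
| Weeks 17-21 | 2 | Week 26 (stop Week 21, tie with Week 34) | 1 | relabelled |
| Week 22 | 2 | Week 34 | 1 | unused |
| Weeks 23-24 | 1 | Week 34 | 0 | stays in Week 26 |

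Over the 25 stop weeks (0 to 24) there are 110 scheduled visits. Of these, 17 fall within 25 days and keep their slot. The other 93 are collapsed (7 + 24 + 20 + 16 + 6 + 6 + 10 + 2 + 2); 25 are used and 68 are not.

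**Week 26 boundary.** Week 26 is day 183, so it stays on-therapy only if last dose is on or after day 183 − 25 = 158. Week 22 is day 155 (28 days before) and Week 23 is day 162 (21 days before). Week 26 therefore leaves its row for 23 of the 25 stop weeks. It is unused for 16 of them (Weeks 0-14 and 22) and relabelled for 7 (Weeks 15-21).

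**ECG.** Only Weeks 26 and 34 compete. For last dose at Week 4 (day 29) the target is day 92; Week 26 is 91 days away and Week 34 is 147. Week 26 is used, although it is 183 − 29 = 154 days after last dose. The same holds for every last dose up to Week 21, with Week 34 unused. At Week 22 the target is day 218; Week 34 (21 days away) beats Week 26 (35 days away).

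**Would slotting by study day be enough?** For vital signs, each Table 5 visit up to Week 26 has its own window. For weight, Week 12 (day 85) falls in the Week 13 window (75 to 102) and collides with nothing. For labs it is not enough: day 85 falls in the Week 8 window (44 to 85) and day 141 in the Week 16 window (86 to 148). All four tables also end the Week 26 window at last dose + 25 days and give Week 34 no day range.

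**The case against.** The strongest defence is that the rule may be deliberate. It sits beside a different efficacy rule and says outright that study day is not used. Its footnotes speak of stopping study treatment, not of leaving the study. The 25-day boundary is used throughout the SAP for adverse events, medications and person-time. Keeping off-drug safety data out of on-drug rows is a legitimate aim, and that part stands.

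A reader might infer that the rule is left over from before Amendment 2, when stopping product meant leaving the study. SAP 2.3.1 still speaks of withdrawal from the study for intolerance, whereas 2.3.2 says such subjects are followed. SAP 11.6.1 describes a return 8 weeks later, but Protocol 5.5.3 says the same of subjects who leave active participation. This is suggestive, not proof. In either case, separating off-drug data does not require merging visits on a 63-day target.

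Four stronger readings are also tempting, and the documents do not support them.

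- *Every later visit is collapsed.* Visits within 25 days of last dose keep their slot, and last doses at Weeks 23-24 keep Week 26.
- *Both the Week 26 and Week 34 records are lost for any last dose up to Week 14.* This holds for vital signs, weight and labs, with Week 14 a tie. It fails for ECG, where Week 26 is used under the wrong label.
- *The later course of these subjects disappears.* All lab, vital-sign and ECG data are listed. Adverse events are classified by onset date, and notable QTc abnormalities are counted at any time after baseline.
- *The efficacy result is at risk.* HbA1c and FPG are slotted by study day regardless of drug status.

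The plan also expects few discontinuations, and its safety analyses are descriptive.

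**Conclusion.** The point holds for by-visit safety summaries. With on-time visits, 93 of 110 scheduled post-discontinuation visits fall into one mislabelled slot and 68 are not summarised. The Week 26 record leaves the Week 26 row for every last dose at Week 22 or earlier. Week 26 safety tables, including Table 3.344, therefore omit subjects last dosed more than 25 days earlier, while the Week 26 HbA1c and FPG analyses include them.

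The figures rest on nominal visit days, and they count each stop week once. They are not a forecast of subjects or records affected, because the documents do not give the timing of discontinuations. Cases near a boundary or tie can move within the ±3-day window. For example, a Week 26 visit on day 180 after last dose on day 155 is exactly 25 days later and stays on-therapy. The tie at a last dose in Week 21 could go to Week 34 if that nominal follow-up visit is taken to match the slot, since 11.3.3 ranks a matching nominal visit above the earlier date.

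This is a fault in a stated rule for secondary safety displays. It does not bear on the primary conclusion and is worth correcting before programming is final.

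**What to change.** In SAP 11.3.2 and 11.3.4:

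1. For subjects who stop product but stay in the study, slot post-therapy vital-sign, weight, lab and ECG records by study day to the Table 5 visits, with an on-/off-therapy flag on each record.
2. Replace the last dose + 25 days upper limit of the Week 26 safety windows with a fixed day, for example day 211 as for HbA1c, and define Week 34 as later than day 211.
3. Add Week 12 and Week 20 lab windows, so that those Table 5 labs do not compete with Weeks 8 and 16.
4. Keep the 8 Week Follow-up slot only for subjects who withdraw from the study under Protocol 5.5.3.
5. Present Week 26 safety summaries, including Table 3.344, both on-therapy and overall.

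If the sponsor prefers to keep off-drug data apart, the flag achieves that without losing visits. The cost is SAP wording, some programming, and an extra on-/off-therapy column in the affected tables. The data are already scheduled for collection.

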11.3.3. Multiple Evaluations

After all the records have been slotted based on therapy period and study day, if there are multiple valid records for an assessment within an assigned analysis visit, only one of these records will be used for summary statistics and analyses. The record to be used is determined using the following hierarchy (in decreasing order of priority):

- the record closest to the target visit day
- the record with an original nominal visit that matches the analysis visit
- the record earliest in time for post-baseline assessments; for baseline, it is the record latest in time

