
ALT \geq5xULN and <8xULN and bilirubin <2xULN without symptoms believed to be related to liver injury or hypersensitivity, and who can be monitored weekly for 2 weeks.
 
OR
 
ALT \geq3xULN and <5xULN and bilirubin <2xULN without symptoms believed to be related to liver injury or hypersensitivity, and who can be monitored weekly for 4 weeks.
	
 • Notify the GSK medical monitor within 24 hours of learning of the abnormality to discuss subject safety. • Subject can continue study treatment • Subject must return weekly for repeat liver chemistries (ALT, AST, alkaline phosphatase, bilirubin) until they resolve, stabilise or return to within baseline • If at any time subject meets the liver chemistry stopping criteria, proceed as described above • If ALT decreases from ALT \geq5xULN and <8xULN to \geq3xULN but <5xULN, continue to monitor liver chemistries weekly. • If, after 4 weeks of monitoring, ALT <3xULN and bilirubin <2xULN, monitor subjects twice monthly until liver chemistries normalize or return to within baseline.

References

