8.2.9.1. Chemistry, Hematology and Urinalysis

Laboratory parameters include the following tests: hematology, chemistry and urinalysis. Established or generally acknowledged methods, normal ranges, and quality control procedures will be supplied by central lab for the study records.

Hematology parameters used in summaries include complete blood count with red blood cell indices, white blood cell count with differential, and platelet count. Chemistry parameters (including lipids) used in summaries include blood urea nitrogen (BUN),

potassium, aspartate aminotransferase (AST), total and direct bilirubin, creatinine, sodium, ALT, total protein, calcium, chloride, alkaline phosphatase (ALP), albumin, bicarbonate, uric acid, gamma glutamyl transferase (GGT), estimated glomerular filtration rate (eGFR), and lipids (including total cholesterol, LDL-C, HDL C, triglycerides, free fatty acids). Urinalysis include specific gravity, pH, glucose, protein, blood and ketones by dipstick and microscopic examination (if blood or protein is abnormal). Note that white blood cell absolute count was not collected in the study.

All laboratory parameters will be summarized, for each treatment group, at every scheduled assessment time point using descriptive statistics and presented graphically. In addition, for hematology and chemistry laboratory parameters, change from Baseline in these quantitative tests will be summarized by treatment group and at every scheduled assessment postbaseline time point. Shift tables providing the number and percentage of subjects with indicated shifts (normal, abnormal not of clinical concern, abnormal of clinical concern) in their results from baseline to each scheduled postbaseline assessment will also be presented for all hematology and chemistry parameters.

Additionally, the number of subjects with laboratory values of potential clinical concern will be summarized by treatment group and scheduled assessment time point for hematology and chemistry. The criteria for laboratory values of potential clinical concern are detailed in [Appendix 7: Values of Potential Clinical Importance](#).

A summary of laboratory values of potential clinical concern will be provided for liver function tests, including ALT, AST, and total bilirubin. The criteria for liver function tests of potential clinical concern are detailed in [Appendix 7: Values of Potential Clinical Importance](#).

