
* Week 26 is the end of treatment visit for those subjects completing the study per-protocol. For subjects who withdraw early from study treatment, the end of treatment visit will be assigned to an analysis visit based on the visit slotting algorithm using study day and therapy phase.
 
** Week 34 is the 8 week post-treatment follow-up visit for those subjects completing the study per-protocol. The 8 Week Follow-up Visit is the 8 week post-treatment follow-up visit for those subjects who withdraw early from study treatment. Both visits will be assigned based on the visit slotting algorithm using therapy phase.
 
*** The target study day for the 8 Week Follow-up Visit for subjects who withdraw early from study treatment is set to be 9 weeks (63 days) after last dose to correspond with the timing of the 8 week post-treatment follow-up for subjects completing the study per-protocol (where last dose is at Week 25 and the follow-up visit is at Week 34).
		

For lab assessments:

Scheduled Visit	Target Study Day of Visit	Slotting Intervals
Pre-therapy		
Week -2	-14	Not applicable
On-therapy		
Week 1	8	2 to 18 days
Week 4	29	19 to 43 days
Week 8	57	44 to 85 days
Week 16	113	86 to 148 days

Scheduled Visit	Target Study Day of Visit	Slotting Intervals
Week 26 (End of Treatment Visit)*	183	149 to (last dose date + 25 days)
Post-therapy		
Week 34**	239	>Last dose date + 25 days
8 Week Follow-up Visit**	Last dose date + 63 days***	>Last dose date + 25 days

* Week 26 is the end of treatment visit for those subjects completing the study per-protocol. For subjects who withdraw early from study treatment, the end of treatment visit will be assigned to an analysis visit based on the visit slotting algorithm using study day and therapy phase.
 
** Week 34 is the 8 week post-treatment follow-up visit for those subjects completing the study per-protocol. The 8 Week Follow-up Visit is the 8 week post-treatment follow-up visit for those subjects who withdraw early from study treatment. Both visits will be assigned based on the visit slotting algorithm using therapy phase.
 
*** The target study day for the 8 Week Follow-up Visit for subjects who withdraw early from study treatment is set to be 9 weeks (63 days) after last dose to correspond with the timing of the 8 week post-treatment follow-up for subjects completing the study per-protocol (where last dose is at Week 25 and the follow-up visit is at Week 34).
		

For immunogenicity assessments:

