3.143.	Safety		On-therapy Injection Site Reaction over Time		
3.144.	Safety		Summary Characteristics of On-therapy Injection Site Reactions		
3.151.	Safety		On-therapy and Post-therapy Liver Events Identified by a Customized MedDRA Query		
3.161.	Safety		On-therapy and Post-therapy Pancreatitis and Pancreatic Cancer		
3.162.	Safety		On-therapy and Post-therapy Adjudicated Pancreatitis Events		
3.171.	Safety		On-therapy and Post-therapy Atrial Fibrillation and Atrial Flutter Adverse Events		
3.181.	Safety		On-therapy and Post-therapy Pneumonia Adverse Events Reported by the Investigator		

Safety : Tables					
No.	Population	IDSL / TST ID / Example Shell	Title	Programming Notes	Deliverable [Priority]
3.182.	Safety		On-therapy and Post-therapy Pneumonia Adverse Events Identified by a Customized MedDRA Query		
3.191.	Safety		On-therapy and Post-therapy Diabetic Retinopathy Adverse Events		
3.201.	Safety		On-therapy and Post-therapy Appendicitis Adverse Events		
3.211.	Safety		On-therapy and Post-therapy Malignant Neoplasm Adverse Events Identified by a Customized MedDRA Query		
Lab Assessments					
3.221.	Safety		Change from Baseline in Hematology by Visit		
3.222.	Safety		Change from Baseline in Chemistry by Visit		
3.223.	Safety		Hematology Values of Clinical Concern by Visit		
3.224.	Safety		Chemistry Values of Clinical Concern by Visit		
3.225.	Safety		Liver Function Tests of Clinical Concern by Visit		
3.226.	Safety		Shift in Hematology by Visit		
3.227.	Safety		Shift in Chemistry by Visit		
3.228.	Safety		Urinalysis by Visit		
Vital Signs					
3.231.	Safety		Change from Baseline in Vital Signs by Visit		
3.232.	Safety		Vital Signs of Clinical Concern by Visit		
3.233.	Safety		Shift in Vital Signs of Clinical Concern by Visit		
[ECG]					
3.341.	Safety		Change from Baseline in ECG Values by Visit		
3.342.	Safety		ECG Values of Clinical Concern by Visit		

Safety : Tables					
No.	Population	IDSL / TST ID / Example Shell	Title	Programming Notes	Deliverable [Priority]
3.343.	Safety		Overall ECG Interpretations by Visit		
3.344.	Safety		Shift in ECG Values of Clinical Concern from Baseline to Week 26		
3.345.	Safety		ECG QTcF and QTcB Results of Notable Abnormalities at any time post-baseli		
Immunogenicity					
3.351.	Safety		Positive Immunogenicity Results for Anti-Albiglutide Antibody Positive Subjects by Visit		
3.352.	Safety		Positive Immunogenicity Results for Anti-Albiglutide Antibody Positive Subjects by Therapy Phase		

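### The laboratory and liver value-of-concern tables keep one record per wide visit window, chosen by date, so peaks at unscheduled retests usually go uncounted; add any-time worst-value rows

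*SAP*

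**What the plan says.** SAP 11.3.2 covers every safety and efficacy parameter summarized by visit. It assigns records to visits by therapy period and study day: "For all records (including unscheduled visit records, early withdrawal records and repeat visit records". Where several valid records share a window, SAP 11.3.3 adds that "only one of these records will be used for summary statistics and analyses". First choice is "the record closest to the target visit day", then a matching nominal visit, then the earliest post-baseline record.

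SAP 8.2.9.1 states that "the number of subjects with laboratory values of potential clinical concern will be summarized by treatment group and scheduled assessment time point for hematology"; the same sentence covers the chemistry panel. Tables 3.223 (hematology) and 3.224 (chemistry) follow that layout, and Table 3.225 is titled "Liver Function Tests of Clinical Concern by Visit". SAP 11.7.1 sets the Table 3.225 rows for ALT and AST at 2, 3, 5, 8 and 10×ULN, plus ≥3×ULN with total bilirubin ≥2×ULN.

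The laboratory windows in SAP 11.3.4 are long; the Week 26 window runs "149 to (last dose date + 25 days"). Safety records more than 25 days after last dose are post-therapy. For these, "For subjects who terminate study treatment early, all post-therapy period records will be assigned to the 8 Week Follow up Visit", a slot whose target is last dose plus 63 days. Protocol Table 5 meanwhile takes chemistry and hematology from subjects who have stopped study drug at Weeks 4, 8, 12, 16, 20, 26 and 34.

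For ALT from 3 to below 8×ULN with study drug continued, Protocol Appendix 3 requires that "Subject must return weekly for repeat liver chemistries". QTc is the only one of these parameters with an any-time post-baseline table (SAP 8.2.10.2, Table 3.345).

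**The concern.** Picking the record nearest the target day suits means and changes from baseline. It suits a table of extreme values less well. Such a table asks whether a subject ever crossed a threshold, and the rule ignores the size of the value.

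Hepatotoxicity is a named potential risk in Protocol Table 2. The protocol retests raised ALT weekly, so a peak is most likely to appear in those samples, and the nearest-day rule usually removes them from the graded counts. No inferential testing is planned on safety variables (Protocol 9.4.2). These descriptive tables are therefore the planned comparison of laboratory excursions between the liquid and lyophilized products.

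**Working it through.** **The plan's own figure.** Week k has target day 7k + 1. Week 34 is Day 239 and Week 25 is Day 176. 239 − 176 = 63 days, which agrees with the stated offset for the 8-week follow-up slot.

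**Laboratory window widths (SAP 11.3.4), last day − first day + 1**
- Week 1: 18 − 2 + 1 = 17 days
- Week 4: 43 − 19 + 1 = 25 days
- Week 8: 85 − 44 + 1 = 42 days
- Week 16: 148 − 86 + 1 = 63 days
- Week 26: last dose Day 176, so the window ends on Day 176 + 25 = 201; 201 − 149 + 1 = 53 days

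**Which record wins.** Visits have a ±3 day window. A scheduled draw inside it is at most 3 days from target, so any other record 4 or more days from target loses. Retests spaced weekly from the scheduled draw are at least 7 − 3 = 4 days off target, so they always lose. In the Week 16 window, take a scheduled draw on Day 113 and retests at +3 days and then weekly (Days 116, 120, 127, 134, 141, 148). Day 113 is kept and all 6 retests are dropped. The same pattern drops 2, 3, 5 and 3 retests in the Week 1, 4, 8 and 26 windows.

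A retest can win. If the scheduled visit is on Day 110, 111 or 112 and a retest falls on Day 113, the retest is used. A record alone in its window is also used.

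**Example.** ALT is 3.5×ULN on Day 113, which triggers weekly retests, and 9×ULN on Day 127. Both days lie in 86–148. The distances from target are 0 and 14, so Day 113 is kept. Table 3.225 counts the subject at ≥2× and ≥3×ULN and omits the subject at ≥5× and ≥8×ULN.

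**Post-therapy samples after early stopping.** Last dose at Week w is Day 7w + 1. The samples affected are the Protocol Table 5 draws later than Day 7w + 1 + 25, with visits taken on their target days. One is kept.

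| Last dose | Scheduled post-therapy draws | Not tabulated |
|---|---|---|
| Week 0 | 7 | 6 |
| Weeks 1–4 | 6 | 5 |
| Weeks 5–8 | 5 | 4 |
| Weeks 9–12 | 4 | 3 |
| Weeks 13–16 | 3 | 2 |
| Weeks 17–22 | 2 | 1 |
| Weeks 23–24 | 1 | 0 |

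For a last dose at Week 4 (Day 29), post-therapy starts after Day 54 and the slot's target is 29 + 63 = Day 92. The draws fall on Days 57, 85, 113, 141, 183 and 239. Day 85 is nearest and is the only one tabulated. Completers have no chemistry or hematology panel at Week 34, only lipids and eGFR, so nothing is lost for them.

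**Other windows.** ECG windows are 21, 21, 77 and 81 days. Vital-sign windows are 7 days for Weeks 2–11 and mostly 11–17 days afterwards.

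**The case against.** The case on the other side has several parts.

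- **Serious liver harm is counted by arm elsewhere.** A value of 9×ULN is a liver stopping event with its own eCRF page. SAP 8.2.7.7 presents investigator-identified liver events by treatment group, and Table 3.151 adds a MedDRA-query summary. Tables 3.51 and 1.4 cover AEs leading to discontinuation and reasons for stopping treatment. ALT ≥3×ULN with bilirubin ≥2×ULN (>35% direct, or fractionation unavailable) is an SAE under Protocol Appendix 5. This stands: a reader who infers that the harm vanishes from every arm-level table would be wrong. None of those displays, however, counts subjects by laboratory threshold.
- **The draw that triggers retesting is usually the record kept.** The ≥3×ULN row then already holds the subject, and so does the single ALT criterion of >3×ULN in Table 3.224. This also stands, and it confines the ALT shortfall mainly to the 5, 8 and 10×ULN rows. An example starting below 3×ULN at the scheduled draw would look more striking, but it does not meet the weekly-retest trigger.
- **Unscheduled records are slotted and sometimes chosen.** It is tempting to say that retests never reach a table, and SAP 11.3.2 and 11.3.3 do not support that.
- **Vital signs do not share the problem to the same degree.** Their windows are mostly narrow, and the documents order no vital-sign retests.
- **Late post-therapy samples say less about the formulations.** They are more than 25 days after last dose, and Protocol 6.9 gives a half-life of about 5 days, with therapeutic concentrations persisting 3 to 4 weeks. This reduces the importance of the second part of the point.
- **The rule is the same in both arms, and values of concern are listed (Listings 33–35).** The documents give no reason to expect the omission to favor one product. Listings still leave the reader to count by hand.

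**Conclusion.** The point holds for Tables 3.223–3.225. It bears most on the higher graded rows of Table 3.225 and on the combined ALT and bilirubin row. As written, those rows can understate maximum values, because laboratory tests have no counterpart to the any-time QTc table.

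The size is known per subject and not for the trial. The documents do not say how many subjects will have retests or will stop study drug and stay on. The 13% in the sample-size section covers early withdrawal or loss to follow-up, which is a different group. A reader might infer that most post-treatment labs are lost in general. That is true only for a last dose up to about Week 16; the loss is half for Weeks 17–22 and nil after that.

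The figures assume scheduled draws within 3 days of target, a last dose on Day 176 for the Week 26 width, and on-target visits for the post-therapy counts. The primary analysis is unaffected. This is an inexpensive improvement to the safety comparison.

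**What to change.** - Keep the nearest-record rule in SAP 11.3.3 for means, change from baseline and the existing by-visit rows.
- In Tables 3.223, 3.224 and 3.225, add two rows per criterion: worst value at any time on-therapy and worst value at any time post-therapy. Use all scheduled and unscheduled records. Do the same in Table 3.342 for ECG parameters other than QTc.
- Count ALT ≥3×ULN with bilirubin ≥2×ULN on the same basis, and state whether both values must come from the same sample.
- State in SAP 11.3.3 that any-time summaries, including Table 3.345, are exempt from the single-record rule; the SAP is silent on this.
- Leave the vital-sign tables as they are.

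The cost is SAP wording and modest programming, with no new data. Counts of abnormal values may rise, and the table footnotes should say that the new rows include unscheduled records.
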